8 INTERVENTION DISCONTINUATION

The study treatment doses will be stopped for any of the following reasons:

- The subject experiences a hypersensitivity or suspected allergic reaction to study treatment
- Subject consent for participation is withdrawn
- The subject experiences a medical emergency that necessitates discontinuation of study treatment
- The subject experiences a medical emergency that necessitates unblinding of the subject's treatment assignment
- At the discretion of the Principal Investigator or the Sponsor for other medical reasons

The reason for discontinuation of study treatment must be recorded in the subject's study worksheets and entered in the study database eCRF. For all subjects who discontinue study treatment, safety data will be collected at subsequent follow up visits until Day 365 +/- 30 days visit (except for those that have withdrawn their consent).

9 STATISTICAL CONSIDERATIONS

9.1 General Design Issues

For all analyses, the primary outcome will be derived from changes in test scores between enrollment and the morning of surgery (baseline), Day 1 post CEA (12-25 h post-op) (eCD) and Day 30 +/- 5 days after CEA or Day of Post-Operative clinical visit (dCD). Neuropsychometric assessment at baseline, will allow screening for MCI and determining if there is a change in cognitive performance from recruitment to operative day due to statin alteration. The intention to treat principle will be used for all analyses. All of the analyses will be performed in two general ways. 1) Significant neurocognitive change for both CEA will be defined compared to an appropriate reference group frequency matched for age, education level, pIQ, and type of anesthetic or sedation. Significant eCD will be defined as performance: (1) $\geq 2SD$ worse than reference group in two or more cognitive domains or (2) $\geq 1.5SD$ worse than the reference group in all cognitive domains tested.

The following data will be kept for patients having CEA: demographic and risk factor variables (age, gender, race, a history of hypertension, diabetes, level of glycosylated hemoglobin, previous myocardial infarction, previous CEA, ApoE genotype, pre-morbid IQ, MCI), degree of carotid stenosis, all additional cerebrovascular workup (i.e. Intracranial MRA, SPECT scanning, angiography, etc.), previous surgeries/anesthetics, laboratory values, all standing medication names (statin usage), doses, and

durations, and all neurologic and neuropsychological scores. Data will also be kept on the results of the delirium screen and the post-operative pain scores.

In general, for the continuous variables, a two-sample Student's t-test will be used for comparing means between the two groups, patients with eCD or dCD and those without eCD or dCD. Non-normally distributed variables will be transformed to improve distributional characteristics. In particular, neuropsychometric test scores will be subjected to a square root transform that yields values that are approximately normally distributed and provide analytic results using parametric tests that are similar to those obtained by non-parametric analysis of the untransformed values. Non-parametric techniques will be used for any variables for which suitable transformations cannot be found. Dichotomous variables will be analyzed using a χ^2 test. Multiple linear and logistic regression models will be used to adjust for the risk factors that are out of balance ($p < 0.10$) between groups. Logistic regression analysis will be used to determine whether any demographic or risk factors other than statin regime significantly affects outcome. Since post-operative pain >4 adversely affects performance, change scores for each test will be obtained using the patients in the reference group, with average pain scores less than 4 as the cutoff value (18).

Missing Data

When data are missing completely at random (MCAR), i.e. when the probability that an outcome is missing does not depend on any outcomes, statistical inference based on completely observed data is valid. If data are missing at random (MAR), i.e. when the probability that an outcome is missing depends on the observed outcomes (such as observed outcome at baseline), inference based on complete data is not valid. We will first check whether the data are MCAR by fitting logistic models for missing data indicators. For example, at the end of the study, the dependent logistic variable is the indicator of whether neuropsychometric test is missing, and the explanatory variables are the outcome at baseline. An insignificant test of the global null hypothesis will confirm MCAR. Assuming the data are not MCAR, we will attempt to obtain bias-corrected estimates under MAR, and we will conduct sensitivity analyses under "non-ignorable missingness".

Interpretation of Results

We anticipate that patients, who are on a sub-maximal statin regimen, will experience more eCD and dCD than patients on a pre-existing maximal statin regimen or randomized to a maximal statin regimen. We anticipate that patients who are randomized to atorvastatin 10mg will experience more eCD and dCD than patients randomized to atorvastatin 80mg. We anticipate that simvastatin will provide more neuroprotection than atorvastatin or rosuvastatin measured by lower incidences of eCD and dCD at comparable statin doses for lipid lowering. Conclusions regarding the arm of statin naïve patients may be somewhat underpowered depending on the number of statin naïve patients we see. Results will be interpreted with according caution. We expect the randomized nature of the trial to randomly distribute patients with regard to age, diabetes, educational level, pIQ, MCI, perioperative delirium and ApoE-e4, but now have accounted for these in the statistical plan and also include long-term outcomes out to a year as well. Post-hoc assessments will also examine whether the primary findings regarding eCD and dCD apply to subgroups of patients but these analyses will be viewed as hypothesis generating only.

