2.1.2 Statins & Cognition

The impact of statins on baseline cognition remains controversial. A study by Hajjar et al. concluded that statins are associated with better cognitive outcomes in elderly populations (19). Similarly, there is evidence statins may also improve cognition (20) through multiple mechanisms, including their action on eNOS (21). While some have suggested that statins may have a deleterious effect on cognition (22, 23), one large literature review suggests otherwise (24), concluding that no significant cognitive impairment can be concluded. A review by Golomb et al. addresses many of the issues related to the deleterious effects of statin and specifically simvastatin therapy (25, 26). The PROSPER study was an observational study in which 5,804 were evaluated at six different time points using four neuropsychological performance tests (27). They concluded that there was neither benefit nor detriment to the cognition of patients on pravastatin. However, the jury is still out on whether the adverse effects are significant for a large percentage of patients or are just rare occurrences. Whatever the case, our previous work strongly suggests that simvastatin is more neuroprotective than atorvastatin in CEA patients (13). While we do not have sufficient numbers of patients to comment on the comparative efficacy of less commonly prescribed statins, it appears that the lipophilic and small molecule size of simvastatin, may make it more effective at penetrating the blood brain barrier than atorvastatin, which although lipophilic, is significantly larger. We have also identified two important demographic factors which independently increase the risk of eCD: age >75 years, and diabetes mellitus (28). Genetic polymorphisms may also confer increased risk with the possession of the ApoE-ε4 (29, 30) allele being the best characterized, but complement cascade (13), phosphodiesterase (31) polymorphisms perhaps playing a role as well. The consequences of eCD after CEA is significant, with a higher risk of early mortality, with statins appearing to attenuate this difference in mortality (2).

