Delirium is a syndrome consisting of a number of symptoms including an acute fluctuating disturbance in consciousness/attention, a change in cognition (memory deficit, disorientation, language disturbance), and a disruption in sleep-wake cycle. A considerable number of predisposing factors have been identified including: older age, cognitive impairment, cardiac failure, cerebrovascular disease, depression, sensory impairment, dehydration, malnutrition, and drug/alcohol dependence. Delirium can also be precipitated by metabolic disarray, medications, infection, and stress. While the incidence of delirium in patients undergoing some highly invasive vascular surgical procedures can be as high as 15%, the incidence in patients undergoing less invasive procedures such as asymptomatic carotid endarterectomy, appears to be no greater than 1.5%(47). Nevertheless, while less common than MCI, delirium, if present, can severely impact assessment of acute cognitive injury like eCD. Thus we will use the Confusion Assessment Method (CAM) to screen for it (48) in all CEA patients as well as all spine surgery controls, both at 24h and 30d. This instrument has been validated for use by nonpsychiatrists and can be performed in 5 minutes with high reliability. Nine questions are quickly addressed and if the patient has inattention (feature 2) that is acute in onset or fluctuating (feature 1) and either disorganized thinking (feature 3) or altered level of consciousness (feature 4) they will be considered delirious. Patients with delirium at any time point or MCI at study onset will be identified using the criteria outlined above, and these data will be analyzed in the univariate and multivariate models planned for the specific Aims.

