9.2.1 Treatment Assignment Procedures

The randomization design will be stratified by center, previous use of statin and in random blocks of 4 and 6. The randomization process will be supported by the Statistical Analysis Center (SAC) at the Mailman School of Public Health at Columbia University. SAC will provide a central secure web-based randomization data system. All trials supported by the SAC employ central randomization that takes place in real-time. In other words, the patient's treatment assignment is made at the moment of randomization, based on probabilities calculated according to the randomization scheme, and communicated to the recruiting site via a central source (i.e. a secure web site).

- Patients on maximum dose of one of the three statins will be maintained on that dose (ARM 1). This arm will contain 225 participants.

- Those patients on submaximal doses of the 3 study statins will be randomized to their current dose plus placebo or their current dose plus the additional milligrams necessary to bring to raise them to the maximal daily dose of simvastatin (40 mg) or atorvastatin (80 mg) or rosuvastatin (20 mg) depending on which statin they are already on, (ARM 2). There will be 337 participants maintained at their current dose and 338 raised to the maximum dose of their statins.
- If patients are statin naïve, then they will be randomized to either atorvastatin 10 mg or 80 mg daily (ARM 3). ARM 3 will have 50 participants in each arm.

The randomization will be performed automatically by the web-based data system. No one will have access to unblinded treatment information on a regular basis other than the packaging pharmacy. All handling of study medication will take place using blinded bottle codes. It is not expected that serious adverse events will require revelation of treatment assignment, but the study web site will provide for online unblinding in emergencies. Revelation of treatment assignment will be available only to authorized users, who will be required to provide a clinical justification for unblinding. Each case of unblinding will be addressed by study personnel to ensure access to unblinded treatment assignment information is limited, and that such incidents are limited to circumstances where it is necessary for the health of the patient.

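### Adjustment covariates are picked by a p<0.10 screen between undefined groups, delirium after surgery is to enter the models, and center is not a stated model term: fix a baseline covariate set in advance

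*Combined protocol and SAP*

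**What the plan says.** **The screen.** Section 9.1 (General Design Issues) states: "Multiple linear and logistic regression models will be used to adjust for the risk factors that are out of balance", the test being p<0.10 between groups; section 9.5 repeats the rule. Earlier in the same paragraph, t-tests are described as "comparing means between the two groups, patients with eCD or dCD and those without eCD or dCD". No other pair of groups is defined there.

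**The primary model.** Sections 9.2 and 9.5 make logistic regression with eCD as the response the primary analysis for all aims. Neither names a covariate.

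**Factors said to be covered.** The interpretation paragraph of 9.1 expects randomisation to spread age, diabetes, education, premorbid IQ, "MCI, perioperative delirium and ApoE-e4, but now have accounted for these in the statistical plan". No model specification shows how.

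**Delirium.** Section 2.1.5 identifies patients with delirium at any time point, screened at 24 hours and 30 days, or with MCI at study onset, and says "these data will be analyzed in the univariate and multivariate models planned for the specific Aims".

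**Design and prognostic variables.** Section 9.2.1 states: "The randomization design will be stratified by center, previous use of statin and in random blocks of 4 and 6". No analysis section lists center as a term. Section 2.1.2 reports "two important demographic factors which independently increase the risk of eCD: age >75 years, and diabetes mellitus", and section 2.1.5 reports eCD in 3.0% of simvastatin users and 16.0% of atorvastatin users.

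**The concern.** A confirmatory analysis should have its covariates fixed before the outcome is seen. Here they depend on a significance test, and the text does not settle which groups are tested.

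- If the outcome groups are meant, the result itself helps choose the model.
- If the randomised groups are meant, any imbalance is chance by construction. The screen then picks factors by accident and can pass over those the protocol itself calls predictive.

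Either way the adjusted estimate cannot be written down in advance. Arm 2 has an interim look at 0.66 of 675 participants (about 446) and a final look (section 9.3). The screen could choose different covariates at each, so the two boundaries would be applied to statistics from different models.

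Delirium after surgery follows treatment and could be affected by it. Adjusting for it could remove part of the effect under study. Leaving out center, and leaving statin type, age and diabetes to a screen, gives up power that the collected data could supply.

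The screen matters in another way for objectives 2 and 4, which include non-randomised comparisons such as Arm 1 against the raised-dose group of Arm 2. There it is the only stated control of confounding, and a real confounder at p=0.11 would be left out.

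**Working it through.** **1. The plan's own figure.** Section 9.2 gives 338 v 337, power 0.80, alpha 0.05 and a detectable reduction of 46.7%, but neither the control rate nor the sidedness. The normal approximation is power = Φ{[(p0−p1) − 1.96·√(2p̄(1−p̄)/n)] / √[(p0(1−p0)+p1(1−p1))/n]}. With n≈337.5, p0=0.145 and p1=0.145×0.533=0.0773, this is Φ{(0.0677−0.0474)/0.0241} = Φ(0.84) ≈ 0.80. The figure therefore needs a control rate of 14.5% two-sided (11.7% one-sided). At the roughly 15% that section 2.2 gives for asymptomatic CEA, two-sided power is 81.5%. The figure fits a documented rate but cannot be reproduced from stated inputs alone.

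**2. How often the screen picks something by chance (randomised-groups reading only).** Section 9.1 lists 11 demographic and risk factors to be recorded, or 12 with degree of stenosis. If they are independent:
- expected number flagged: 11×0.10=1.1 to 12×0.10=1.2
- chance of at least one: 1−0.9^11=0.686 to 1−0.9^12=0.718

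**3. Cost in Arm 2.** Simulation settings: 675 patients, ten equal centers, blocks of 4 and 6 within center and statin type, true OR 0.49, 13 independent candidate factors of which three are predictive, 1,500 runs per setting. The statin mix is 94:66:12 (atorvastatin, simvastatin, rosuvastatin; section 2.1.5). Assumed, not in the documents: rosuvastatin eCD equal to atorvastatin, log odds of 0.5 to 0.6 for the predictors, and center SD of 0 to 0.8 on the logit scale. The screen (between randomised groups) is compared with a fixed model of center, statin type and the three predictors.

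| Center SD | Type I, screen | Type I, fixed | Power, screen | Power, fixed | Gain (points) |
|---|---|---|---|---|---|
| 0 | 4.4% | 5.4% | 74.4% | 77.8% | 3.4 |
| 0.5 | 3.6% | 5.1% | 74.6% | 79.1% | 4.5 |
| 0.8 | 3.6% | 5.3% | 76.3% | 81.3% | 5.0 |

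Monte Carlo error on the type I figures is about 0.6 points. Part of the gain reflects the screened test running below its nominal 5%. At least one factor was flagged in 76% of trials. Screening on the outcome in the same runs gave type I error of 4.4%, 3.7% and 3.6%, and power of 74.5%, 76.0% and 75.9%.

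Two further simulations compared an unadjusted model with one adjusted for statin type, age over 75 and diabetes. Power rose from 81.7% to 84.2% (3,000 trials, 14.8% v 7.9% eCD, assumed odds ratios of 2) and from 79% to 82% (1,500 trials, same scenario, assumed prevalences of 40% and 30%).

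**4. Delirium.** Inputs: 1.5% incidence (the upper figure in section 2.1.5 for asymptomatic CEA), assumed eCD of 14% v 7.46%, and every delirious patient assumed to have eCD. The overall OR is (0.0746/0.9254)/(0.14/0.86)=0.495. Among control patients without delirium, risk is (0.14−0.015)/0.985=0.127.
- If treatment lowers delirium in proportion, treated risk is (0.0746−0.008)/0.992=0.067. The risk difference falls from 6.5 to 6.0 points and the OR stays at 0.495.
- If treatment prevents all delirium, treated risk is 0.0746 and the OR becomes 0.555.
- At 5% delirium, all prevented, the OR would be 0.77.

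**5. Room in the models.** At 14.5% v 7.73%, Arm 2 yields 337×0.145+338×0.0773≈75 events. Nine center terms plus six others leave 75/15=5 events per term, too few for unpooled fixed center effects. Arm 3 has 100 patients. At an assumed 15% to 20% in both groups that is 15 to 20 events, and fewer if treatment works.

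**The case against.** The strongest reply is that the text is general and several harsher readings go beyond it. Much of this stands.

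- **Selection on the outcome.** A reader might infer that the plan certainly chooses covariates by the result. The wording permits this but does not establish it. The 69% to 72% figure belongs to the other reading. It also assumes independence, which diabetes and glycosylated hemoglobin plainly lack, and it counts a list of data to be kept, not a list of covariates.
- **The primary result depends on the screen.** The sections naming the primary analysis give no covariates, so the screen may be supportive only. The plan does not say.
- **Age and diabetes are left out.** Section 9.1 says that they are accounted for. The fair criticism is that no model shows how.
- **Pain as a covariate.** The pain passages in 2.1.1, 9.1 and 9.5 mainly concern reference patients. Whether pain in CEA patients enters a model is unclear.
- **Both strata are ignored.** Previous statin use as yes/no is constant within Arm 2 and within Arm 3. Center is the stratum that matters there.
- **Intervals are too wide.** This does not hold for the conditional log odds ratio. In the second of the two further simulations its mean standard error rose from 0.257 to 0.267 with adjustment. Power rose because the estimate moved from −0.71 to −0.77.
- **Delirium.** Being analyzed in the models need not mean that the treatment effect is adjusted for it, and at 1.5% the bias is small.

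The central point survives: the groups are undefined, the covariates are not fixed, and center is not named.

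**Conclusion.** The point holds as a problem of specification with a modest statistical cost. The covariate set should be fixed before unblinding, and the plan should say which model is primary. A reader might infer an inflated false-positive rate. The simulations do not show one: under the randomised-groups reading the screened test ran at 3.6% to 4.4% against a nominal 5%. The loss is about 2 to 5 points of Arm 2 power, under covariate and center effects that the documents do not give. Delirium bias is small at 1.5% and would matter only if delirium were considerably more common and strongly affected by treatment. The main gain from the change is that the model cannot be chosen after the data are seen and stays the same at the interim and final looks.

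**What to change.** Delete the p<0.10 rule in sections 9.1 and 9.5 and put in its place:

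- **Arm 2, interim and final looks alike:** logistic regression of eCD on assigned regimen, with center (random intercept, or small centers pooled), statin type, age and diabetes; ApoE-e4 optional. Report the standardised risk difference with its confidence interval.
- **Arm 3:** assigned dose and age only, because events are few.
- **Non-randomised comparisons in objectives 2 and 4:** a prespecified confounder list, for example center, statin type where it is not the exposure, age, diabetes, ApoE-e4, and education or premorbid IQ. Deleting the screen without this would leave these comparisons with no stated confounder control.
- **Eligible covariates:** only those measured before the first study dose or that treatment cannot affect. A ban on anything measured after randomisation would be wrong, since section 6.2.3 collects baseline assessments after randomisation and allows the ApoE sample at any time.
- **Delirium after surgery:** keep it out of the primary model; show it descriptively and in one sensitivity analysis.
- **Pain:** state whether pain in CEA patients is a covariate at all; if so, treat it like delirium.

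The cost is wording in the analysis sections. Every variable is already collected, and neither the sample size nor the visit schedule changes.

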This aspect of statin neuroprotection has never been explored in detail in humans. Less lipophilic statins than simvastatin may become effective at high concentrations, underscoring the importance of generating a putative dose-response curve. While about 90% of patients at Columbia University Medical Center are already on a statin, we have reason to believe that in more underserved (lower income, less educated) populations, such as those at Montefiore Medical Center in Bronx NY and the University of New York in Buffalo NY, a smaller percentage of patients will be on statins prior to enrollment, and those that are likely to be on diminished doses that preliminary data suggests are less neuroprotective (55). Thus, if we can demonstrate a benefit in the total population, we may also have identified a pre-op therapy that would be particularly important for underserved populations. A second potentially innovative aspect of the proposal concerns the surveillance of systemic inflammation in this population. If certain statin regimes protect against eCD and dCD, whether these regimes are associated with less (or marked changes in) systemic inflammation will be important mechanistic data regardless of the result.

Our previous grant (R01 AG17604) was funded from July 1, 2003 to June 30, 2013. Over the 10 years the grant was funded, and the 15 years we have been studying patients having treatment for CEA, there has been a dramatic change in the incidence of eCD. We have investigated the reason(s) for this change. This analysis has been the primary outcome of this funding period. During our previous R01 grants, we enrolled 878 patients: 620 having CEA, 68 having CAS, and 190 reference patients having either “simple” spine surgery (155 patients) or coronary artery angiography or stenting (34). Of the 620 CEA patients, 559 had full neuropsychometric analysis completed pre- and post-operatively. Of these 559 patients, 231 were symptomatic patients undergoing CEA and 328 were asymptomatic. Symptomatic status refers to whether the patient

has a history of stroke or transient ischemic attack prior to surgery. We significantly surpassed our enrollment goals for all granting periods. All of the neuropsychometric data were analyzed, except for the data from 8 symptomatic and 4 asymptomatic patients because they experienced a peri-operative stroke. We utilized our reference population to account for practice effect and learning due to repeated neuropsychometric testing.

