9.2 Sample Size and Randomization

Power Analysis

All of the aims will use logistic regression with presence of eCD as the response variable as the primary statistical analysis. A separate independent analysis for dCD will also be performed. Power calculations used data simulations (1000 simulations for each) with power=0.8, $\alpha=0.05$, and expected rates of eCD

based on existing preliminary data. For the comparison between subjects in arm 1 with a maximal dose (N=225) and those in arm 2 beginning with a sub-maximal dose and increasing to a maximal dose (N=338), the estimated minimum detectable effect size corresponds to a 65% reduction in eCD in the former cohort vs. the latter. For the comparison in between subjects in arm 2 beginning with a sub-maximal dose and increasing to a maximal dose (N=338) and those staying at the sub-maximal dose (N=337), the estimated minimum detectable effect size corresponds to a 46.7% reduction in eCD in the former cohort vs. the latter. For the comparison between subjects in arm 3 with 80 mg of atorvastatin (N=50) and those with 10 mg of atorvastatin (N=338), the estimated minimum detectable effect size corresponds to a 91.3% reduction in eCD in the former cohort vs. the latter.

Rationale for Sample Sizes

As per the power analysis above, the 1000 targeted patient enrollment is reasonable considering the aims of this study. We anticipate approximately 350 patients will be scheduled for CEA per year from the six participating institutions (Columbia-Presbyterian, St. Luke's Roosevelt, Cornell University, Valley Hospital, Montefiore Medical Center, and Buffalo Medical Center). Approximately 80% are anticipated to be asymptomatic, leaving 280 per year.

Expecting an approximate 75% recruitment rate, 210 eligible asymptomatic patients will be enrolled each year from the six sites. Over five years, this rate allows for 1000±50 patients to be enrolled. Based on our previous R01 grant, we estimate that a) 225 patients will already be on a pre-existing maximal statin regimen of simvastatin, atorvastatin, or rosuvastatin, b) 675 patients will be on a sub-maximal statin regimen of simvastatin, atorvastatin, or rosuvastatin, and c) 100 patients will be on no pre-existing statin regimen.

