9.4 Outcomes

We have defined our primary outcome on Z-scores based on the mean and standard deviation of cognitive testing change in scores of a surgical reference group before and after surgery (12-25h and 30 days postop/ Day of PO clinical visit).

The cognitive testing has been divided by cognitive domains and the patients are considered to have postoperative early cognitive dysfunction (eCD) based on two criteria to account for both focal and global/hemispheric deficits. Consequently anyone with:

- (a) $\geq 2SD$ worse than reference group in two or more cognitive domains or
- (b) $\geq 1.5SD$ worse than the reference group in all cognitive domains tested will be considered a primary outcome.

If the subjects experience stroke or TIA peri-operatively, they will be considered as having reached a secondary OUTCOME in the study.

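### A non-significant missingness test is taken to establish MCAR, and only rejection brings in the MAR and non-ignorable analyses of eCD and dCD

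*Combined protocol and SAP*

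**What the plan says.** The Missing Data text of Section 9.1 sets out a sequence.

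- Under MCAR, "statistical inference based on completely observed data is valid". Under MAR, the same text says, complete-data inference is not valid.
- MCAR is checked first, with logistic models for the missing-data indicators. In the example given, "the explanatory variables are the outcome at baseline".
- The decision rule is: "An insignificant test of the global null hypothesis will confirm MCAR".
- The safeguards come after that: "Assuming the data are not MCAR, we will attempt to obtain bias-corrected estimates under MAR", with sensitivity analyses under non-ignorable missingness in the same sentence.

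Section 9.5 repeats the definitions of MCAR and MAR but gives no test and no remedy. The analysis affected is the primary one (Section 9.2, repeated in 9.5): "All of the aims will use logistic regression with presence of eCD as the response variable as the primary statistical analysis".

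eCD is defined only by Z-scores (Sections 3, 9.1 and 9.4). On stroke, Section 9.4 says: "If the subjects experience stroke or TIA peri-operatively, they will be considered as having reached a secondary OUTCOME in the study". No section says how eCD or dCD is coded for a patient who has died or cannot be tested. Sections 9.1 and 9.5 apply intention to treat to all analyses but do not address such patients.

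**The concern.** A non-significant test is absence of evidence, not evidence of MCAR. The named predictor is also measured before surgery. The plausible reasons for a missing test at 12 to 25 hours or at 30 days arise afterwards: neurological injury, delirium, sedation, death. If those reasons go with cognitive decline but only weakly with baseline score, the test cannot see them.

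The rule matters because it decides the analysis. When the test does not reject, the plan treats complete cases as valid, and the only analyses that could show sensitivity to lost outcomes are not called for. For an endpoint that measures brain injury, the patients most likely to be untestable are those most likely to be events. Unequal loss between randomized groups can hide or create a treatment effect.

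**Working it through.** **Inputs from the documents.** ARM 2 has 337 and 338 patients, with a detectable reduction of 46.7% at 80% power and alpha 0.05 (Section 9.2). In the earlier programme, "Of the 620 CEA patients, 559 had full neuropsychometric analysis completed pre- and post-operatively" (Section 2.1.5), so 620 − 559 = 61 lacked full testing, and 61/620 = 9.8%. That figure includes missing pre-operative tests, so it is only a rough guide to lost outcomes. Section 9.2 states no dropout allowance.

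**Step 1. Recover the control rate.** Section 9.2 does not give it. For two proportions with n ≈ 337.5 per group, power = Φ{[|p1 − p2|√n − 1.96√(2p̄(1 − p̄))] / √(p1(1 − p1) + p2(1 − p2))}, where p2 = 0.533 × p1. At p1 = 0.1448, p2 = 0.0772 and p̄ = 0.1110:

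(0.0676 × 18.37 − 1.96 × 0.4443) / 0.4417 = 0.84, so power = 0.80.

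The stated figure is therefore reproduced at a control rate of about 14.5% (two-sided test assumed). Section 2.2 gives about 15% for asymptomatic patients, where power is 0.815. The working rates below, 14.5% v 7.7%, are assumptions obtained in this way.

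**Step 2. How often the rule declares MCAR when it is false.** ARM 2 trials were simulated, 3,000 per scenario, with about 10% missing. Missingness depended on eCD itself, and a likelihood-ratio test of missingness on baseline score was run at 5% (the plan states no level).

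| Correlation of baseline score with decline | Trials in which MCAR is declared |
|---|---|
| 0 | about 95% |
| 0.1 | 89% to 93% |
| 0.3 | 42% to 79% |

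The ranges cover 30% of eCD cases lost in both groups, 50% lost in both, and 50% control v 20% treated, with 5% to 7% of non-cases lost.

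**Step 3. What complete cases then show.** If a share m of eCD cases and a share k of non-cases is missing, the observed rate is p(1 − m) / [p(1 − m) + (1 − p)(1 − k)].

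With m = 0.5 in control, 0.2 in treated, and k = 0.06:
- Control: 0.0725 / (0.0725 + 0.8037) = 8.3%.
- Treated: 0.0618 / (0.0618 + 0.8674) = 6.7%.
- Apparent reduction: 1 − 0.0665/0.0827 = 19.6% (19.0% in simulation), against a true 46.7%. Power is about 0.10.

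With no true effect (14.5% in both groups) and the split reversed:
- Control: 0.1160 / (0.1160 + 0.8037) = 12.6%; treated 8.3%.
- A false reduction of about 34% to 35% appears, and the null is rejected in 41% of simulated trials.

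With equal loss (m = 0.5 and k = 0.05 in both groups), the observed rates are 8.2% v 4.2%. The relative reduction is nearly kept (about 48%), but power falls to about 0.55. Purely random loss of 9.8% gives power 0.76.

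**Step 4. Size of the stroke question.** Section 2.2 puts peri-operative stroke below 1.5%, and 0.015 × 675 = 10.1. Section 2.1.5 reports 0.0% in earlier asymptomatic statin users. The range for ARM 2 is therefore about 0 to 10. At the upper end, counting strokes as events rather than leaving them out gives:
- 5 v 5: control (0.145 × 332 + 5)/337 = 15.8%; treated (0.0773 × 333 + 5)/338 = 9.1%; reduction 42.3%, power 0.75.
- 10 v 0: control (0.145 × 327 + 10)/337 = 17.0%; treated 7.7%; reduction 54.6%.

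The coding choice can move the estimate by about −4 to +8 points from 46.7%.

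**The case against.** Four defences deserve an answer.

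**The baseline predictor is only an example.** That stands: Section 9.1 speaks of models in the plural, and other predictors could be added. Adding arm would help against unequal loss. In Step 3 the missing fractions are 0.145 × 0.5 + 0.855 × 0.06 = 12.4% and 0.0773 × 0.2 + 0.9227 × 0.06 = 7.1%. A direct comparison has z ≈ 0.053/0.0228 = 2.3, so power is roughly 0.64. That still misses about a third of such trials, and no wider predictor set makes non-rejection a proof.

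**MAR and non-ignorable analyses are planned.** They are, but as the text is ordered they follow only when MCAR is not accepted. If the sponsor meant them unconditionally, the sentence should say so.

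**Missingness tied to baseline alone does little harm.** This is correct. When baseline score drives missingness equally in both groups (odds ratio 1.3 per SD, 9.8% missing), the simulated complete-case reduction was 46.8% to 47.1% against a true 46.8% to 46.9%. The test's power against that mechanism is therefore no measure of harm. The harm comes from outcome-related loss.

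**Stroke patients are not excluded.** This also stands. A reader might infer from Section 9.4 that stroke patients leave the eCD analysis. The text makes stroke and TIA a secondary outcome and removes nobody from Z-score assessment. The earlier analysis did leave such patients out ("except for the data from 8 symptomatic and 4 asymptomatic patients because they experienced a peri-operative stroke", 12 of 559, 2.1%), but that was the earlier programme. Those 12 were among the patients with full testing, so leaving them out was an analysis choice, not missing data.

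**Conclusion.** The decision rule in Section 9.1 is wrong as logic and weak as a check, and nothing elsewhere in the document repairs it. Its size depends on how outcomes are lost, which the documents do not tell us. The 95% and 42% to 79% figures, and the fall from 46.7% to about 19% to 20%, rest on assumed eCD rates, loss splits and correlations. They show what the rule could let through, not what will happen.

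Three stronger conclusions are not supported.

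- A reader might take the earlier stroke rates of 0.0% v 3.1% (Section 2.1.5) to mean that loss will differ by arm. They compare statin users with non-users, and Section 2.2 says every trial patient will receive a statin. They are silent on maximal v sub-maximal dose.
- A reader might see a contradiction with intention to treat. No section excludes a randomized patient from eCD. The plan leaves the principle without a coding rule for untestable patients, which is an omission.
- A reader might conclude that the test is blind to every post-operative cause. That holds only where the cause is unrelated to baseline. At correlation 0.3 the test rejected in 21% to 58% of simulated trials.

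This should be corrected before unblinding.

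**What to change.** 1. Delete the rule in Section 9.1 that a non-significant test establishes MCAR, and align Section 9.5. A missingness model may stay as description, with counts and reasons by arm and visit.
2. Make a MAR method the standard handling of missing eCD and dCD. One choice is multiple imputation by arm using NPT #1, NPT #2, the other post-operative visit, stroke/TIA, CAM, age, diabetes, statin type and center.
3. Always run a delta or tipping-point analysis by arm, whatever any missingness test shows. MAR imputation does not by itself protect against loss that depends on the unseen result.
4. State that patients with stroke or TIA who are tested stay in the eCD and dCD analyses.
5. Add a sensitivity analysis that counts peri-operative stroke, death before testing, and neurological inability to be tested as eCD/dCD = yes.

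Item 5 is proposed as a sensitivity analysis because using it as the primary analysis would redefine the endpoint. With 5 v 5 strokes, power would be about 0.75.

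The cost is SAP wording, modest programming and slightly wider intervals.
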